APPENDIX 9: VENEER/COMPOSITE INTEGRITY

VENEER/COMPOSITE INTEGRITY	
A=	Intact
B1=	Partially missing – one third missing
B2=	Partially missing – two thirds missing
B3=	Partially missing – more than two thirds missing
C4=	All veneer/composite missing

APPENDIX 10: SECONDARY CARIES

SECONDARY CARIES	
A=	Absent
B=	Present

APPENDIX 11: TRAUMA

TRAUMA	
A=	Absent
B=	Present

APPENDIX 12: CLINICAL PULP PATHOLOGY

CLINICAL PULP PATHOLOGY	
A=	Absent
B=	Present

APPENDIX 13: RADIOGRAPHIC PULP PATHOLOGY

RADIOGRAPHIC PULP PATHOLOGY

A=	Absent
B=	Present

APPENDIX 14: PARENTS' ESTHETIC SATISFACTION

1. Which of the following best describes your thoughts overall about the appearance of your child's teeth?
 - a. Very satisfied
 - b. Somewhat satisfied
 - c. Somewhat dissatisfied
 - d. Very dissatisfied
2. If not "very satisfied", which of the following are you concerned about? (circle "yes" or "no" for each subcategory)

a. Shape	1. Yes	2. No
b. Color	1. Yes	2. No
c. Alignment	1. Yes	2. No
d. Spacing between teeth	1. Yes	2. No
e. Crowding of teeth	1. Yes	2. No
f. Speckled/spotted/streaky/irregular/blotchy appearance	1. Yes	2. No
g. Other: _____

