PVSSC are SSC bonded with thermoplastic composites on the roughened or meshwork facial surfaces. It is made from the same SSC used by dentists for many years. Many advantages of these crowns are noted. Parents find the PVSSC's to be esthetically acceptable, hemorrhaging does not affect the resistance or retention, or color of the crown, and there is less chair time needed when compared with alternative restorations.⁶ Nevertheless, no system is without disadvantages. The operator is limited to crimping only on the lingual surface of the crown because crimping the facial may cause the veneer to chip off. This leads to limited adaptability of the crown to the tooth surface. In addition, there are only two shades available, making exact colors matching very difficult for a single tooth. Overall, the PVSSCs cost more money than SCCs or direct resin restorations.⁸ Recently, NuSmile introduced a new type of anterior crowns, the NuSmile ZR. It is made of high grade monolithic zirconia ceramic which provides strength, durability and esthetics characteristics to these crowns.

With the variety of options for restoring anterior primary teeth, it is of interest to evaluate the long term success of PVSSC, zirconia and composite in terms of durability, esthetics and cost effectiveness for the treatment of anterior primary teeth.

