6. STUDY POPULATION

Ninety (90) subjects contributing to approximately 120 to 200 crowns on primary teeth will be recruited from the patient pool of the Center for Pediatric Dentistry who receive care under general anesthesia and enrolled into the study. A maximum of four crowns will be placed in any subject. It is estimated that it will take approximately 24 weeks to place all crowns and complete the baseline examination.

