6.1 Inclusion Criteria

- Patients of record at the University of Washington's Center for Pediatric Dentistry
- Patients in general good health (ASA I)
- Patients aged 5 years old or younger
- Patients in need of at least one preformed crowns, on anterior primary teeth
- Patients undergoing general anesthesia for dental treatment
- Parent or guardian of patient able and willing to provide informed consent

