7.5 Operative Procedures

After the subject's parent/guardian has provided informed consent for participation in the study, patient's sedated procedure will be accomplished. This study will be executed within a comprehensive restorative treatment. A rubber dam will be placed and the crowns will be placed following manufacturers' guidelines, see below.

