10. STUDY ASSESSMENTS

Clinical Assessments will be done at baseline post crown placement; at months 3, 6, 12 and 18; and end of study visit occurring in range of 24 to 30 months from baseline.

Assessments and documentation required at each assessment interval:

• Photographs of selected teeth	Baseline
• Photographs of tooth preparations	Baseline and when possible
• Photographs of cemented crowns	Baseline
• Photographs of occlusal and frontal views	Baseline and when possible
• Assessment of fit	All intervals
• Assessment of positioning	All intervals
• Assessment of proximal contact	All intervals
• Assessment of marginal adaptation	All intervals
• Assessment of color: match , staining/color change	All intervals
• Assessment of time placement	Baseline
• Assessment of gingival status	All intervals
• Assessment of retention	3, 6, 12, 18 and 24 mo
• Assessment of veneer/composite integrity	3, 6, 12, 18 and 24 mo
• Assessment of secondary caries	3, 6, 12, 18 and 24 mo
• Assessment of trauma	3, 6, 12, 18 and 24 mo
• Assessment of clinical pulp pathology	3, 6, 12, 18 and 24 mo
• Assessment of radiographic pulp pathology	24 mo
• Assessment of tooth	All intervals
• Assessment of parents' esthetic satisfaction	All intervals (baseline at 3-month follow up)

Non-recall assessment to be done at the time of tooth/crown lost to study due to trauma. If this was to occur, the patient would be discontinued from study and the justification recorded.

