11.0 DATA ANALYSIS

Descriptive statistics (means, standard deviations, counts, and percentages) will be calculated for all variables. To evaluate if the primary efficacy variables differ by the three treatment groups (NuSmile PVSCC Signature Crowns, NuSmile ZR, and Strip composite crowns), ANOVA or Chi-square tests of association will be performed.

All subjects evaluated at the 6-month interval or beyond and subjects who have lost crowns or teeth will be considered for efficacy. All enrolled subjects defined here as those who have had at least one crown placed will be evaluated for safety. Any missing, unused or false data will be omitted from data analysis.

The primary efficacy variables in this trial are fit, positioning, proximal contact, marginal adaptation, color match, gingival status, crown retention, veneer/composite integrity, secondary caries, occlusal integrity, history of trauma, clinical pulp pathology, parents' esthetic satisfaction. Scores for efficacy variables will be summarized and displayed using descriptive statistics (means, standard deviations, counts, and percentages).

Inferential statistics will be used to detect significant differences in the primary efficacy variables by the treatment status at baseline and at 6, 12, 18, and 24 month follow-up. Statistical differences will be calculated using logistic regression models accounting for within cluster variance using generalized estimating equations (GEE).

Safety variables include Adverse Events and Unanticipated Adverse Device Effects. All subjects that have had crowns placed will be evaluated for safety. Descriptions of occurrences, incidence, severity and required treatments for Adverse Events and Unanticipated Adverse Device Effects Will be summarized and tabulated where appropriate.

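### The parents' esthetic satisfaction item, a primary efficacy variable, asks about all the child's teeth and never about the study crowns, so non-study teeth add noise and can shrink a difference between arms

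*Combined protocol and SAP*

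**What the plan says.** Section 1 states the trial's interest: "it is of interest to evaluate the long term success of PVSSC, zirconia and composite in terms of durability, esthetics and cost effectiveness". Section 11.0 carries the esthetic part into the primary efficacy variables, whose list ends "secondary caries, occlusal integrity, history of trauma, clinical pulp pathology, parents' esthetic satisfaction".

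The only instrument for the parent's view is Appendix 14. Question 1 reads "Which of the following best describes your thoughts overall about the appearance of your child's teeth" and has four answers from very satisfied to very dissatisfied. Question 2 applies to parents who are not very satisfied. It lists shape, color, alignment, spacing, crowding, uneven or spotted appearance, and other. Neither question mentions a crown, a front tooth or a study tooth.

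Four other places bear on what the parent is looking at:

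- Section 6.1 sets the minimum number of crowns: "Patients in need of at least one preformed crowns, on anterior primary teeth".
- Section 6 sets the maximum and the expected total: "A maximum of four crowns will be placed in any subject", and "Ninety (90) subjects contributing to approximately 120 to 200 crowns on primary teeth".
- Section 7.5 gives the setting: "This study will be executed within a comprehensive restorative treatment".
- Section 10 gives the timing of the satisfaction item: "All intervals (baseline at 3-month follow up". The first answer is therefore taken at month 3, after treatment.

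Section 8 only names the item. Nothing elsewhere narrows the question to the crowned teeth.

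**The concern.** The treatment being compared is a type of crown on one to four anterior teeth. The question covers the whole dentition. A parent who is pleased with the crowns but unhappy with other teeth has no way to say so on this form, and neither does a parent with the opposite view. The score is therefore broader than the treatment.

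What is at stake is sensitivity. This is the only parent-reported outcome. If other teeth account for part of the answer, a real difference in how parents see the three crowns will look smaller than it is. A finding of no difference could then mean either that the crowns please parents equally or that the question could not tell them apart. With no pre-treatment answer, earlier views on other teeth cannot be adjusted for. Crown-specific opinions also cannot be recovered afterwards from data collected on this form.

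**Working it through.** The documents state no satisfaction rate, target difference or power, so there is no figure of the plan to reproduce on this point. The check has two parts.

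**1. What the item covers.**
- Arms: 3 × 30 = 90 children, which agrees with Section 5.
- Study crowns per child: 120/90 = 1.33 to 200/90 = 2.22 on average, within the permitted range of one to four (Sections 6 and 6.1).
- Setting: other dental work is expected in the same children (Section 7.5).
- Wording: the child's teeth overall (Appendix 14).

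The item thus takes in non-study teeth. This follows from the wording and needs no assumption. The crown count does not measure the dilution, because parents need not weigh all teeth equally.

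**2. What that could do to a comparison (illustration only).** None of these inputs is in the documents:
- Crown-specific dissatisfaction is p = 10% in one arm and 40% in another.
- A share q of parents, the same in both arms and independent of the crowns, is dissatisfied because of other teeth.
- Either source of dissatisfaction is enough to make the overall answer dissatisfied.
- The four levels are cut into two.
- 30 children per arm all answer, and two arms are compared by a two-sided test at 0.05.

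Observed dissatisfaction = 1 − (1 − p)(1 − q), so the observed difference = 30 points × (1 − q). Power is the normal approximation for two proportions (pooled variance under the null, unpooled under the alternative).

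| q | Observed rates | Difference | Power |
|---|---|---|---|
| 0% | 10% vs 40% | 30 points | 78% |
| 10% | 19% vs 46% | 27 points | 61% |
| 20% | 28% vs 52% | 24 points | 47% |
| 30% | 37% vs 58% | 21 points | 37% |
| 50% | 55% vs 70% | 15 points | 22% |

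A second form of dilution drops the rule that either source is enough. It shrinks the difference between 90% and 60% very satisfied around their fixed mean of 75%. Power goes from 78% with no shrinkage to 52%, 27% and 10% with shrinkage of 25%, 50% and 75%. Starting from 85% vs 50%, it goes from 84% to 59%, 30% and 11%.

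Both forms show the direction of the effect and how quickly power falls at 30 per arm. Neither says how much dilution this trial would have.

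**The case against.** The best defense is that the item may work much as intended. The study teeth are anterior, so they are the teeth a parent sees most and may dominate an overall judgment. Section 6.2 excludes anterior crowding and class III occlusion, which removes some competing reasons for dissatisfaction in the same region. Section 7.4 randomizes by patient and gives all study teeth in a child the same restoration, so the other teeth are balanced between arms on average. Crown-level esthetics are also scored directly through color match and staining at every interval (Section 10, Appendix 5). The trial is a pilot with a convenience sample, thirteen primary variables and no decision rule tied to satisfaction. Overall appearance is itself a legitimate thing to ask parents about.

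Most of this stands, and it limits the point. It does not answer it. Balance between arms prevents a systematic tilt but does not remove noise or attenuation. The Appendix 5 color score is not the parent's opinion.

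A reader might go further and infer that complaints about spacing or crowding can never concern a crown. The documents do not support that: Appendix 2 grades rotation and position, and Appendix 3 grades proximal contact including open spaces, so crowns can affect these features. The accurate statement is that shape, color, alignment, spacing and crowding answers may reflect the crowns or other teeth, and the form cannot tell which.

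**Conclusion.** The point holds as a mismatch between a primary efficacy variable and its instrument: Appendix 14 measures satisfaction with the whole dentition, while the trial compares crowns on one to four anterior teeth. The expected consequence is noise and a smaller observed difference between arms. The size cannot be derived from the documents and may be small. The 30 × (1 − q) illustration and the power figures rest entirely on the assumed rates, the assumed q and the assumed rule for combining the two sources of dissatisfaction.

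Two stronger readings are not supported. A reader might infer that the comparison is biased toward one crown type, but patient-level randomization gives no reason to expect non-study teeth to favor an arm. A reader might also take 1.3 to 2.2 crowns per child as showing that most of the answer concerns other teeth. That would require parents to weigh every tooth equally, which nothing in the documents says. This is a worthwhile and inexpensive improvement, not a flaw that invalidates the trial.

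**What to change.** In Appendix 14, before question 1, add the same four-level question about the front tooth or teeth that were crowned in this study. Identify those teeth by neutral printed wording or a tooth diagram on a form the parent completes. Staff should not point them out: the trial is non-blinded (Section 4), and that would invite courtesy or expectation effects. Direct the question 2 list to the same teeth.

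In Section 11.0, name the crown-specific answer as the efficacy variable for parents' esthetic satisfaction and keep the overall question as descriptive.

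The cost is one more question, a redirected list and one changed line in the analysis section. The form becomes slightly longer. Even with neutral wording, the new question draws some attention to the study crowns among parents who may know which type was placed.
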